8.3.3 CLASSIFICATION OF AN ADVERSE EVENT

8.3.3.1 SEVERITY OF EVENT

All AEs will be graded for severity using the following guidelines.

- **Mild** – Events require minimal or no treatment and do not interfere with the participant's daily activities.
- **Moderate** – Events result in a low level of inconvenience or concern with the therapeutic measures. Moderate events may cause some interference with functioning.
- **Severe** – Events interrupt a participant's usual daily activity and may require systemic drug therapy or other treatment. Severe events are usually potentially life-threatening or incapacitating. Of note, the term "severe" does not necessarily equate to "serious".

8.3.3.2 RELATIONSHIP TO STUDY INTERVENTION

All adverse events (AEs) must have their relationship to study intervention assessed by the principal investigator and co-investigator who examines and evaluates the participant based on temporal relationship and his/her clinical judgment. The degree of certainty about causality will be graded using the categories below. In a clinical trial, the study product must always be suspect.

- **Definitely Related** – There is clear evidence to suggest a causal relationship, and other possible contributing factors can be ruled out. The clinical event, including an abnormal laboratory test result, occurs in a plausible time relationship to study intervention administration and cannot be explained by concurrent disease or other drugs or chemicals. The response to withdrawal of the study intervention (dechallenge) should be clinically plausible. The event must be pharmacologically or phenomenologically definitive, with use of a satisfactory rechallenge procedure if necessary.
- **Probably Related** – There is evidence to suggest a causal relationship, and the influence of other factors is unlikely. The clinical event, including an abnormal laboratory test result, occurs within a reasonable time after administration of the study intervention, is unlikely to be attributed to concurrent disease or other

drugs or chemicals, and follows a clinically reasonable response on withdrawal (dechallenge). Rechallenge information is not required to fulfill this definition.

- **Potentially Related** – There is some evidence to suggest a causal relationship (e.g., the event occurred within a reasonable time after administration of the trial medication). However, other factors may have contributed to the event (e.g., the participant’s clinical condition, other concomitant events). Although an AE may rate only as “possibly related” soon after discovery, it can be flagged as requiring more information and later be upgraded to “probably related” or “definitely related”, as appropriate.
- **Unlikely to be related** – A clinical event, including an abnormal laboratory test result, whose temporal relationship to study intervention administration makes a causal relationship improbable (e.g., the event did not occur within a reasonable time after administration of the study intervention) and in which other drugs or chemicals or underlying disease provides plausible explanations (e.g., the participant’s clinical condition, other concomitant treatments).
- **Not Related** – The AE is completely independent of study intervention administration, and/or evidence exists that the event is definitely related to another etiology. There must be an alternative, definitive etiology documented by the clinician.

8.3.3.3 EXPECTEDNESS

The principal investigators ([name], expert in SLE and [name], expert in non-invasive brain stimulation) will be responsible for determining whether an adverse event (AE) is expected or unexpected. An AE will be considered unexpected if the nature, severity, or frequency of the event is not consistent with the risk information previously described for the study intervention.

8.3.4 TIME PERIOD AND FREQUENCY FOR EVENT ASSESSMENT AND FOLLOW-UP

The occurrence of an adverse event (AE) or serious adverse event (SAE) may come to the attention of study personnel during study visits or the study participant may report AE or SAEs outside of a scheduled study visit.

All AEs including local and systemic reactions not meeting the criteria for SAEs will be captured on the appropriate case report form (CRF). Information to be collected includes event description, time of onset, clinician’s assessment of severity, relationship to study product (assessed only by those with the training and authority to make a diagnosis), and time of resolution/stabilization of the event. All AEs occurring while on study must be documented appropriately regardless of relationship. All AEs will be followed to adequate resolution.

Any medical condition that is present at the time that the participant is screened will be considered as baseline and not reported as an AE. However, if the study participant’s condition deteriorates at any time during the study, it will be recorded as an AE.

Changes in the severity of an AE will be documented to allow an assessment of the duration of the event at each level of severity to be performed. AEs characterized as intermittent require documentation of onset and duration of each episode.

The study coordinator will record all reportable events with start dates occurring any time after informed consent is obtained until 7 (for non-serious AEs) or 30 days (for SAEs) after the 3-month follow up (end of study participation). At each study visit, the study coordinator will inquire about the occurrence of AE/SAEs since the last visit. Events will be followed for outcome information until resolution or stabilization.

8.3.5 ADVERSE EVENT REPORTING

We will be adopting the following table for reporting procedures:

What Event is Reported	When is Event Reported	By Whom is Event Reported	To Whom is Event Reported
Fatal or life-threatening unexpected, suspected serious adverse reactions	Within 24 hours of initial receipt of information	Investigator	
 Local/internal IRBs, DSMB
Non-fatal, non-life-threatening unexpected, suspected serious adverse reactions	Within 48 hours of initial receipt of information	Study Coordinator	
 Local/internal IRBs/Institutional Officials, DSMB
Unanticipated adverse device effects	Within 7 working days of investigator first learning of effect	Investigator	
 Local/internal IRBs
Unanticipated Problem that is not an SAE	Within 7 days of the investigator becoming aware of the problem	Investigator	
 Local/internal IRBs/Institutional Officials,

8.3.6 REPORTING OF PREGNANCY

Pregnancy tests will be administered at the initial screening session as well as before treatment on the first stimulation visit to all women of child-bearing potential. There are no studies that suggest tACS would interfere with pregnancy. However, should a participant become pregnant during the study their participation will be immediately terminated and will be sent to consult with Co-I.

Following withdrawal, the patient will be followed through the 4 week follow-up with the designated clinical assessments to ensure participant safety: HDRS, YMRS, Suicide Questionnaire. Additional measures may be continued if deemed appropriate (e.g., EEG, cognitive tasks, Comparative Pain Scale, Pain Catastrophizing Scale)

8.4 UNANTICIPATED PROBLEMS

8.4.1 DEFINITION OF UNANTICIPATED PROBLEMS (UP)

The Office for Human Research Protections considers unanticipated problems involving risks to participants or others to include, in general, any incident, experience, or outcome that meets **all** of the following criteria:

- Unexpected (in terms of nature, severity, or frequency) given (a) the research procedures that are described in the protocol-related documents, such as the IRB-approved research protocol and informed consent document; and (b) the characteristics of the participant population being studied;
- Related or possibly related to participation in the research
- Suggests that the research places participants or others at a greater risk of harm (including physical, psychological, economic, or social harm) than was previously known or recognized.

8.4.2 UNANTICIPATED PROBLEM REPORTING

If an UE occurs, the IRB will be notified and the study will be adjusted as needed to protect the health and safety of the participants. Depending on the nature of the UE, the research protocol, inclusion/exclusion criteria, and informed consent will be changed to reflect the possibility of this event reoccurring. During this time, no new participants will be recruited and the research procedures for currently enrolled participants will be stopped. Each UE will be recorded and reported throughout the study.

8.4.3 REPORTING UNANTICIPATED PROBLEMS TO PARTICIPANTS

Any new information gained during the study that may affect a participant's willingness to continue participating will be reported to all currently enrolled participants.

9 STATISTICAL CONSIDERATIONS

9.1 STATISTICAL HYPOTHESES

Null hypothesis: There is no difference in changes of alpha frequency power between baseline (Day 1) RSEEG and RSEEG at completion of stimulation (Day 5) between treatment regimens.

Alternate hypothesis: There is a difference in changes of alpha frequency power between baseline (Day 1) RSEEG and RSEEG at completion of stimulation (Day 5) between treatment regimens.

9.1.2 SECONDARY EFFICACY HYPOTHESIS

Null hypothesis: There is no relationship between the changes in alpha frequency power and the changes in depression (using the IDAS and HDRS), pain (using the comparative pain scale and pain catastrophizing scale), and cognition (using the sustained attention task, selective attention task, working memory task, and FSCMC).

Alternate hypothesis: There is a relationship between the changes in alpha frequency power and the changes in depression (using the IDAS and HDRS), pain (using the comparative pain scale and pain catastrophizing scale), or cognition (using the sustained attention task, selective attention task, and working memory task, and FSCMC).

9.2 SAMPLE SIZE RATIONALE

At this point in time, no clinical trial has been completed using tACS to treat SLE. However, the Carolina Center for Neurostimulation has run several trials similar to this, including a clinical trial assessing the use of tACS to treat depression over the course of a 5-day, 40-minute stimulation paradigm (Alexander et al., 2019).

This study is a critically necessary preliminary step in this line of research. The most important aspects of the study are its exploratory analyses, its provision of point- and interval-estimates of parameters of interest, and the logistical feasibility and tolerability information it will provide. The levels of precision of the estimators of interest are important; e.g., based on a previous tACS intervention study (Alexander et al., 2019) with a mean alpha oscillatory difference of ~ 2 and $SD \approx 1.2$ and alpha set at .05, we anticipate $N=20$ per group will provide more than 80% power. The effect size was based off the difference between active tACS and sham stimulation. This study will also provide an initial indication of whether it is plausible that tACS may have beneficial effects for the target lupus population. Based on the anticipated

precision of estimators, power levels of test procedures, availability of research subjects, and stage of this line of research, we believe the study is likely to achieve its specific aims; i.e., there is low risk the study will be uninformative/inconclusive.

9.3 POPULATIONS FOR ANALYSES

Every effort will be made to ensure all enrolled and randomized participants complete all study sessions as described in this protocol. However, *a priori*, we determine that our population for analysis will be a per-protocol analysis dataset, indicating that only those who complete the intervention (i.e., the 5 days of stimulation) will be included in the analysis. For this study, enrolled eligible participants will be randomized to receive 5 consecutive days of stimulation. If a participant completes the intervention (i.e., receives all 5 consecutive days of stimulation), they will be included in all analyses moving forward.

Reasons for missing data (e.g., missing follow-up sessions) and reasons for participant withdrawal will be documented within the master list.

As stated previously in *Section 7 Study Intervention Discontinuation and Participant Discontinuation/Withdrawal*, enrolled participants who do not complete the full intervention will not be included in this analysis. Therefore, with this population for analysis plan, we anticipate having data from at least 45 participants that are eligible for analysis.

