received tACS reported an increase in suicidal ideation from baseline. We will be using the Suicide Item included in the HDRS17 to assess suicide risk. Inclusion criteria states that the patient must be low suicide risk defined as a score of less than 3 on the HDRS17 suicide item, potential participants that have an above “low risk” designation will not be eligible for the study. Additionally, we will administer this as a daily questionnaire to assess suicide risk. In the case suicide risk increases after the screening visit, the participant will be asked to stop the study and will be provided with a referral to UNC Psychiatry and their mental health care or family medical doctor will be contacted. [name], Co-I, will facilitate this process.

Research within our lab has shown that alpha and theta oscillations exist in an antagonistic relationship. Therefore, an increase in alpha oscillations would result in a decrease in theta oscillations (and vice versa). In a previous tACS trial (Alexander et al., 2019), we found that alpha-tACS reduced alpha oscillations over the course of 5 days. We propose that alpha-tACS did this through synchronization of those two areas. Theta-tACS would theoretically work in an orthogonal mechanism to alpha-tACS, by suppressing alpha oscillations, rather than synchronizing it. Theoretically, theta-tACS could exacerbate underlying depression and worsen outcomes. Furthermore, traditional treatments for depression (e.g., antidepressants) run the risk of exacerbating depression symptoms as well. We will be following patients closely throughout the study as well as employ the assistance of a Data Safety and Monitoring Board, which we plan to review our blinded data every 6 months.

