7 STUDY INTERVENTION DISCONTINUATION AND PARTICIPANT DISCONTINUATION/WITHDRAWAL

7.1 DISCONTINUATION OF STUDY INTERVENTION

Discontinuation from the week of stimulation does not mean discontinuation from the study, and remaining study procedures should be completed as indicated by the study protocol. If a clinically significant finding is identified (including, but not limited to changes from baseline) after enrollment, the investigator or qualified designee will determine if any change in participant management is needed. Any new clinically relevant finding will be reported as an adverse event (AE).

The study intervention (i.e., the 5 consecutive days of stimulation) will be discontinued for the following reasons:

- A participant develops increased suicidal risk, as determined by an acute assessment by [name].
- A participant has a YMRS score greater than to 12.
- The participant misses two consecutive days of stimulation.
- The participant misses a single day of stimulation and is unable to make it up at the end of the stimulation week.
- Any clinical adverse event (AE), laboratory abnormality, intercurrent illness or other medical condition, or situation occurs such that continued participation in the study would not be in the best interest of the participant.
- The participant meets any exclusion criteria (either newly developed or not previously recognized).
- A participant wishes to withdraw from further participation for any reason.

If the participant withdraws from the intervention, he/she will be followed through the 4 week follow-up with the designated clinical assessments to ensure participant safety:

- HDRS
- YMRS
- Suicide Questionnaire

Additional measures may be continued if deemed appropriate (e.g., EEG, cognitive tasks, Comparative Pain Scale, Pain Catastrophizing Scale).

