8.2 SAFETY AND OTHER ASSESSMENTS

8.2.1 SAFETY

1. A suicide questionnaire previously used in IRBs #14-0600 and #14-1622 will be used at each session of this study. This questionnaire tracks suicidal ideation and behavior. Participants will be asked to answer whether they have had any thoughts of hurting themselves within the past 24 hours (suicidal ideation, SI) and whether they have hurt themselves within the past 24 hours (suicidal behavior, SB). If a participant admits to experiencing either SI or SB their participation will be stopped immediately and their primary mental health care provider or family physician will be contacted. In the case that they do not see anyone for their depressive symptoms, [name] will assist the participant in seeking medical care
2. The structural MRI to be used for source localization during EEG analysis will be conducted prior to randomization. The results of the T1 weighted sMRI will be reviewed by [name] for incidental findings of malignancy. If any are found, the study team will disqualify patient from study participation and will facilitate contact with providers for medical care per [name] recommendations. Patients will complete the provided MRI screening form provided by the Biological Research Imaging Center (BRIC) prior to the sMRI screening visit.
3. A stimulation adverse effects questionnaire will be administered at the end of each stimulation session. This questionnaire will be used as a safety measure and to collect data on participant experience. This questionnaire has been used in all our previous tACS studies.

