9.4 STATISTICAL ANALYSES

9.4.1 GENERAL APPROACH

All testing described below assumes a significance threshold of $p = 0.05$. All hypothesis tests that are observed to not be statistically significant will be reported as being inconclusive. Continuous data will be described using means and standard deviations, while categorical data will be described using counts/percentages. All statistical estimates of population parameters will be tabulated along with their corresponding confidence intervals (CIs).

Sensitivity analyses will be used to evaluate the robustness of the main results to reasonable perturbations of the statistical models and assumptions used.

[name] will be responsible for statistical computations for data analyses. During the initial data analysis phase, [name] will be blinded to whether data and results are from sham vs active treatment in compliance with the UNC School of Medicine Conflict of Interest Committee proposed financial conflict of interest management plan.

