9.4.2 ANALYSIS OF THE PRIMARY EFFICACY OUTCOME MEASURE(S)

We will perform spectral analysis of resting state EEG from day 1 of stimulation (baseline) to day 5 of stimulation. We will use a general linear mixed-effects model (GLMM) to assess if there is statistically significant interaction between treatment (sham/placebo, theta-tACS and alpha-tACS) and session (baseline/Day 1 of stimulation, day 5 of stimulation, 2-week follow-up, 4-week follow-up). Spectral analysis will be performed with multitapered estimation of the frequency spectrum followed by integration over the classical alpha EEG band (usually 8-12 Hz). In a separate analysis, we will perform spectral analysis of resting state EEG before and after each separate stimulation session. These analyses will be completed on the per-protocol dataset.

In our previous study, which used a 5-day protocol in patients with depression (Alexander et al., 2019), we found that a correlation between the log-transformed baseline alpha power (dB) and the alpha power changes at the end of the intervention (Day 5) in all regions. We chose to use the log-transformed baseline alpha power as a covariate. We will use this same covariate in these analyses as well.

Results from this section will be described in mean decibel (dB) change and presented using spectral images for visualization.

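### The primary EEG comparison is confined to five-day completers, no all-randomised analysis is named, and EEG after stopping is optional, so the effect of the exclusions may be impossible to check.

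*Combined protocol and SAP*

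**What the plan says.** **Population.** Section 9.3 fixes a per-protocol set in advance: "only those who complete the intervention (i.e., the 5 days of stimulation) will be included in the analysis". Section 9.4.2 applies it to the primary model: "These analyses will be completed on the per-protocol dataset". Intention-to-treat appears only in the abbreviation list. Section 9.4.1 adds a general promise, "Sensitivity analyses will be used to evaluate the robustness of the main results to reasonable perturbations of the statistical models and assumptions used", but names no population. Section 7.3 says the analysis plan allows for missing data; section 9 states no missing-data assumption.

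**After stopping.** Section 7.1 lists the reasons for ending stimulation. They include increased suicidal risk, a YMRS score above 12, adverse events, missed sessions and the participant's wish. It says that stopping stimulation is not leaving the study and that "remaining study procedures should be completed as indicated by the study protocol". It then requires only HDRS, YMRS and the suicide questionnaire through week 4, and adds: "Additional measures may be continued if deemed appropriate (e.g., EEG, cognitive tasks". Other sections end participation for some of the same reasons. Section 2.3.1: "In the case suicide risk increases after the screening visit, the participant will be asked to stop the study". Section 8.2.1: "If a participant admits to experiencing either SI or SB their participation will be stopped immediately"; it also ends participation if mania develops during the stimulation week. On suicidal thoughts or behaviour, section 9.4.4 refers instead to an acute assessment where necessary.

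**Codes.** Section 6.2.1 provides 72 codes, each tied to an arm, and reassigns a code after any withdrawal or loss to follow-up. Section 6.1.2 calls the code specific to the participant. Section 7.2 replaces those who received part of the intervention, but not those who received all of it and left later.

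**The concern.** Randomisation makes the arms comparable as assigned. Once inclusion depends on finishing five days, the comparison is between those who finished in each arm, and these groups can differ if treatment affects who stops. Several reasons in section 7.1 could depend on treatment. Section 2.3.1 says theta-tACS could in theory worsen depression. It also reports increased suicidal thoughts in 4 sham participants, and in none given tACS, in a similar study. It does not say that any of them stopped, or when the events occurred, so this makes arm-related stopping plausible and no more.

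Section 9.2 counts "its provision of point- and interval-estimates of parameters of interest" among the most important aspects of this pilot. Those estimates could be shifted by who completes, and no named analysis would show it.

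Code reuse is a smaller and separate matter. A replacement takes the leaver's arm, and staff who enter the code can see that two people share a treatment, though not which one. If section 6.2.1 is followed literally, a completer lost later stays in the analysis while the same code passes to a successor.

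**Working it through.** **1. The plan's own figure.** Section 9.2 gives a difference of about 2, SD about 1.2, alpha 0.05 and 20 per group, for power above 80%. A two-sided, two-sample t test gives 0.999 at 20 per group and 0.993 at 15. The claim is reproduced. The planned effect is 2 / 1.2 = 1.67 SD, assuming that 1.2 is the SD of the change.

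**2. Bias from excluding stoppers.** In an arm, let p be the share who stop and g the stoppers' mean Day 5 change minus the completers' mean, in SD units. The mean over all randomised is the completer mean plus p × g. The completer contrast between arms A and B is therefore off by |pA × gA − pB × gB|. The documents give neither p nor g, so the values below are assumptions.

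- 10% v 20% stopping, gap 0.5 SD in both arms: |0.05 − 0.10| = 0.05 SD
- 10% v 30% stopping, gap 1 SD in both arms: |0.10 − 0.30| = 0.20 SD
- 30% stopping in both arms, gap 1 SD in one and 0 in the other: 0.30 SD (an extreme case)

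**3. Effect on inference.** Section 4.4 ends enrolment at 45 participants who complete the study, or 15 per arm if balanced. The standard error of one unadjusted contrast is √(2/15) = 0.365 SD. Type I error follows from the noncentral t distribution with 28 df and noncentrality bias / 0.365. The last column is bias × 1.2 / 2.

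| Bias (SD) | Type I error | 95% CI coverage | Share of planned difference |
|---|---|---|---|
| 0 | 5.0% | 95.0% | 0% |
| 0.05 | 5.2% | 94.8% | 3% |
| 0.20 | 8.3% | 91.7% | 12% |
| 0.30 | 12.5% | 87.5% | 18% |

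**4. Would changing the population be enough?** No. Under missing-at-random, a stopper with only a Day 1 recording adds essentially nothing about Day 5. A simulation of the 0.20 SD case (30% v 10% stopping, gap 1 SD and unrelated to baseline, 24 per arm) gave a bias of 0.20 SD both for completers only and for an all-randomised likelihood analysis.

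**5. Is an all-randomised analysis affordable?** Take 24 per arm, Day 5 EEG obtained from everyone, and no effect in stoppers. The difference becomes 2 × (1 − p), which is 1.8, 1.6 or 1.25 at 10%, 20% or 37.5% stopping. The t-test power is 0.999, 0.995 or 0.94. The last figure falls to about 0.88 if the added mixture variance is counted.

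**6. Cost of ending code reuse.** In simulations to the first 45 five-day completers, with 10% to 30% stopping per arm and no reuse, the average standard error was 0.2% to 1.3% above an equal split with blocks of 3. With reuse it was at the equal-split value. Section 6.2.1 describes no blocking. Without it the excess was 0.8% to 1.6%, against 0.8% with reuse, so ending reuse costs up to 1.016 / 1.008 − 1 = 0.8%. At 30% stopping, the chance of 45 five-day completers within 72 randomised is 93% either way. Under section 4.4's rule, with an assumed 10% later loss, it is 59% without reuse and 58% with it.

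**The case against.** The strongest defence is that this is a declared pilot aimed at target engagement, for which a completer analysis fixed in advance is a recognisable choice. The intervention lasts five days, section 5.5 lets one missed session be made up, and reasons for withdrawal and attendance at each session are recorded. Few may be excluded, and the losses would be visible. All of that stands, and it limits the likely size. It does not restore the randomised comparison: fixing the set in advance prevents choosing it from the data, and nothing more. Recording reasons shows who left, not what their EEG would have been.

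The illustrations can also be challenged. The 8.3% needs threefold differential stopping and a full 1 SD gap, and the 12.5% is more extreme still. Both describe one unadjusted contrast, whereas section 9.4.2 plans a baseline-adjusted treatment-by-session interaction. That is fair, and they should be read as bounds on assumed inputs.

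Section 7.1 can be read as a general rule followed by a safety minimum. On that reading it still does not say whether a stopper's Day 5 EEG is expected.

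A reader might infer that reissuing codes breaks the randomised comparison or merges two people's data. The documents do not support this. The successor receives a randomly assigned and still blinded arm, and sections 9.4.6 and 10.1.3 refer to participant identification numbers and dummy identifiers for the data.

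**Conclusion.** The concern holds on three points of text. The primary comparison is conditioned on completion and no all-randomised analysis is named. The primary endpoint is optional after stopping. Sections 6.2.1, 6.1.2 and 7.2 disagree on code reuse and replacement.

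The size is unknown. On the assumptions shown, type I error for one contrast runs from 5.2% to 12.5%, with the top an extreme case. Against the planned difference the bias is 3% to 18%, so it matters most if the true effect is small or null.

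Two stronger readings should be resisted. The gap between 72 and 45, which is 27/72 = 37.5%, might be taken as the expected stopping rate. It may include screen failures, since sections 1.1 and 4.1 speak of recruiting up to 72, and losses after Day 5, since section 4.4 counts participants through three months. Nor does redefining the population remove the bias: without later EEG from stoppers, the result is essentially the completer one.

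This should be fixed. Confidence is high on the text and low on the size.

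**What to change.** - **Sections 9.3 and 9.4.2:** name an analysis of all randomised participants with a Day 1 pre-stimulation resting EEG, as assigned, using all available later resting EEG and stating the missing-at-random assumption. Report it beside the completer analysis, preferably as primary.
- **Section 7.1:** seek the already scheduled Day 5 resting EEG from stoppers who remain in the study and agree. The previous step depends on this.
- **Section 9.4.1:** name one sensitivity analysis that shifts stoppers' unobserved Day 5 change by 0 to 1 SD, separately by arm.
- **Sections 6.2.1, 6.1.2 and 7.2:** reconcile replacement and code reuse. At minimum, do not reissue the code of anyone who stays in the analysis. Taking the next unused code is an option: there are 72 codes for up to 72 participants, so supply does not require reuse.
- **Sections 7.1, 2.3.1, 8.2.1 and 9.4.4:** reconcile who remains in the study after stopping. Which clinical rule applies is for the investigators.

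The cost is wording, one analysis and a few recordings. The downsides are some dilution from partial exposure, reliance on missing-at-random where Day 5 EEG is absent and, if reuse ends, slightly less balanced completer counts. That imbalance adds up to about 1.3% to the standard error with blocks of 3, or 0.8% without blocking.
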